Clinic visit for term (37-41 6/7 week) pregnant patients 18-50 years old with decision by primary obstetrics provider for induction of labor and patient is deemed candidate for outpatient cervical ripening per BWH Cervical Ripening Protocol by their primary obstetrics provider

- Inclusion:
 - Vertex presentation
 - Induction of labor indicated for maternal or neonatal reasons
- Exclusion
 - Prior cesarean section
 - Non-English-speaking participants
 - No need for cervical ripening (Bishop score >6, >2cm dilated)

Patient is scheduled for outpatient cervical ripening per BWH protocol. Her outpatient obstetrical provider informs her of the study. Study staff will attempt to contact patient once appointment is made and discusses study with patient and answer any questions she may have. If patient is unable to be contacted they will still be approached for the study when they arrive for outpatient cervical ripening after study has been introduced by a clinician/provider at their visit.

At time of her cervical ripening appointment on CWN 3, CWN 5 labor and delivery, or at [name] if patient remains interested, she is consented by physician investigators. Questions answered.

RANDOMIZATION: 1:1 Cook catheter Vs Dilapan-S per outpatient protocol.

Cervical ripening with either agent per randomization.

If unable to place cervical ripening device, further cervical ripening per provider preference by one of options already approved per BWH outpatient cervical ripening protocol

Return to L&D within 24hrs of device placement (return visit will be scheduled through hospital EMR as is current BWH outpatient cervical ripening protocol) or earlier with any concerning symptoms (vaginal bleeding, fever, rupture of membranes, labor, decreased fetal movement, etc), as detailed in existing BWH outpatient cervical ripening protocol

When returned to L&D, device removed or confirmed expelled. Sterile vaginal exam performed by blinded examiner (3rd year, chief resident, or further in training- i.e. Fellow or Attending), blinded to study arm.

Paper patient satisfaction survey to be given to patient at this time by study staff for written completion by subject

Further induction of labor per primary labor and delivery team.

4. Subject Selection

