Women will be booked for outpatient cervical ripening per their primary obstetrics provider. Typically, cervical ripening is scheduled by the primary provider within the week prior. Outpatient ripening is currently performed by a variety of methods (Cook balloon, Dilapan-S and misoprostol) at the primary provider's discretion. The eligibility for each of these methods is the same, thus all patients scheduled for outpatient ripening in current clinical practice are potentially eligible for this study. At the time patients are scheduled, the scheduling provider (nurse or MD) may inform the patient about the study. The scheduling provider will then let the study staff know if patients are interested and if they would like to be contacted for further information or if they are not interested and would prefer not to be further contacted by study staff. Study staff will attempt to contact interested patients to answer any questions they have about the study. This will not be a pre-screening call as anyone who is scheduled for outpatient cervical ripening is eligible for the study. Study staff will also monitor the outpatient ripening appointments booked through the EPIC schedule. Study staff will contact patients who are scheduled for outpatient cervical ripening appointments within 48 hours of their appointment via telephone to discuss the study and answer any questions and assess interest. If the patient is unable to be contacted, a clinician/provider at their cervical ripening visit will introduce the study to the patient and if they agree to be approached, study staff will then approach them for possible enrollment. Once the patient arrives for their scheduled outpatient cervical ripening appointment on CWN3, CWN5 Labor and Delivery triage, or [name] study staff will review the study, answer any questions and informed consent will be obtained. If the patient had not heard about the study previously, a provider/clinician will introduce the study to the patient when patient arrives and ask if study staff can approach them. If the patient agrees,

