Secondary maternal outcomes will be measured including patient satisfaction with cervical ripening method via a survey administered after return to labor and delivery (Appendix B), cesarean delivery rate, time from admission on labor and delivery to delivery, maternal length of stay, and indication for cesarean delivery. We will also calculate a composite cervical ripening success score. Success will be defined by a lack of any of the following: failure of placement of cervical ripening agent, unscheduled return to medical care, rupture of membranes, vaginal bleeding, or need for further cervical ripening after the initial agent is removed. We will also calculate a composite maternal morbidity outcome. Morbidity will be defined by any of the following: higher-order laceration, blood transfusion, endometritis, wound infection, venous thromboembolism, hysterectomy, ICU admission or death. These outcomes will also be stratified by parity. We will also evaluate rates of regional analgesia use in both groups.

A composite neonatal morbidity will be calculated including any one of the following: culture-proven neonatal sepsis, neonatal blood transfusion, hypoxic-ischemic encephalopathy, intraventricular hemorrhage grade 3 or 4, or therapeutic hypothermia. We will also analyze NICU admission, NICU admission for greater than 48 hours, and neonatal length of stay.

This study design is a non-inferiority randomized control trial with 1:1 randomization comparing Dilapan-S to Cook Catheter with the primary outcome of change in Bishop score. We have defined a non-inferiority margin of 2 with a standard deviation of 3 consistent with prior literature. A Type I α error of 0.05 was selected. Assuming 80% power and a two-sided P value we would need 39 patients in each arm for a total of 78 patients; however, prior studies⁶ reported a 10% failure of placement rate (due to patient intolerance of exam or provider failure) to account for this and the small risk of loss to follow-up, we will increase the sample size by 15% and will include 45 participants in each group for a total of 90 participants.

For statistical purposes, intent to treat analysis will be performed. Non-parametric measures will be used for statistical analysis. These models will also be adjusted for parity.

10. Monitoring and Quality Assurance

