- 4) Confirm cephalic presentation and normal fluid volume. This can be done via formal or bedside ultrasound. If a formal ultrasound is performed within the week but not on the day of induction, cephalic presentation should be confirmed by physical exam or bedside ultrasound.

Prior to ripening (misoprostol only):

- 1) NST must be performed and must be reactive without excessive uterine activity (no more than 2 contractions in 10 minutes).

Foley Balloon Placement:

- 1) This can be placed in any setting, though ideally in the office-based ambulatory setting in the afternoon.
- 2) Either a 30 cc Foley (inflated up to 35 cc) or a Cook catheter can be used.
- 3) Balloons can be placed digitally or with a speculum (at provider discretion). If a speculum is used, the cervix should be cleansed with betadine prior to placement.
- 4) Only 2 attempts at a balloon should be performed. If placement fails after 2 attempts, the provider can place Dilapan instead or abandon office-based ambulatory mechanical ripening.
- 5) After placement, the Foley catheter tail can be taped to the thigh, tucked into the vagina or tied off and trimmed.
- 6) No monitoring is needed after placement.
- 7) If the Foley catheter falls out before the scheduled inpatient appointment, the patient should be instructed to throw out the Foley catheter. She can stay home until her scheduled appointment (unless labor, rupture of membranes or other concerns require an office or hospital visit).

Dilapan Placement:

- 1) Cervix is visualized with a speculum and cleansed with betadine.
- 2) Dilapan rods are placed using a ring forceps. Ideally 3-5 rods should be placed. No more than 5 rods should be used. Rods can be moistened with saline or sterile water to aid in placement.
- 3) A moistened gauze can be placed in the vagina to help keep the Dilapan in place if desired (though not necessary).

- 4) The number of Dilapan and gauzes left in the patient should be clearly documented in the EPIC record.
- 5) No monitoring is needed after placement.
- 6) If the Dilapan(s) or sponge(s) fall out before the scheduled inpatient appointment, the patient should be instructed to collect all the rods/sponges in a plastic bag or take a picture of the rods/sponges and throw them away. She can stay home until her scheduled appointment (unless labor/rupture of membranes or other concerns arise).

Misoprostol Placement:

- 1) 50 mcg of oral misoprostol is administered

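### Intent to treat is the only analysis set for the non-inferiority claim, although women with failed placements may receive the other device; a supportive per-protocol analysis should be pre-specified

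*Combined protocol and SAP*

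**What the plan says.** Section 9 (Statistical Analysis) describes a non-inferiority trial with change in Bishop score as the primary outcome, a margin of 2 points and an assumed SD of 3. On the analysis set it has one sentence, "For statistical purposes, intent to treat analysis will be performed", followed by "Non-parametric measures will be used for statistical analysis" and an adjustment for parity. No per-protocol, as-treated or other second set appears anywhere in the document.

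The sample size paragraph of the same section cites "a 10% failure of placement rate (due to patient intolerance of exam or provider failure"), a single rate that is not split by arm. It continues "to account for this and the small risk of loss to follow-up, we will increase the sample size by 15" per cent, which takes 39 per arm to 45.

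Three places describe what follows a failed placement:

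- Section 3, study flow: "If unable to place cervical ripening device, further cervical ripening per provider preference by one of options already approved" under the hospital's outpatient protocol.
- Section 5, on the methods in use: "Outpatient ripening is currently performed by a variety of methods (Cook balloon, Dilapan-S and misoprostol").
- Appendix A, under Foley Balloon Placement (which also covers the Cook catheter): "If placement fails after 2 attempts, the provider can place Dilapan instead or abandon office-based ambulatory mechanical ripening".

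Failed placement enters an outcome definition once. The secondary ripening-success composite in section 9 lists "failure of placement of cervical ripening agent" among the events that rule out success.

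**The concern.** In a superiority trial, crossover between arms usually works against the sponsor's claim. In a non-inferiority trial it works for the claim, because it shrinks the difference that the confidence limit has to exclude. Here the route from comparator to test device is written into the care pathway that the trial adopts, and the plan itself expects placement failures.

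The plan can be read as asking either of two questions. One concerns the policy of offering a device, with whatever fallback follows. The other concerns the device once it is in place. The stated purpose in section 1, helping patients and providers choose between mechanical agents, fits both. ITT answers the first. If some women cross over, ITT alone gives a reader little basis for judging the second. If a second set is chosen only after the data are seen, it will be open to the charge of selection on results.

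**Working it through.** **Inputs from section 9.** Margin 2, SD 3, two-sided 5% level (taken here as one-sided 2.5% for the non-inferiority test), 80% power, 39 per arm raised to 45, and 10% placement failure.

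**Inputs assumed.** Crossover rates and the true device difference, neither of which the documents give.

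**1. The plan's own sample size.** The normal formula gives 2 × [3 × (1.96 + 0.84)/2]² = 35.3, so 36 per arm. A two-sided t-test gives 36.3. Dividing 36.3 by 0.955, the usual efficiency of the rank-sum test, gives 38.02, so 39. The 0.955 is my assumption, but it fits the stated non-parametric analysis. The inflation is 39 × 1.15 = 44.85, so 45. The plan's figures are reproduced on that basis.

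**2. Dilution under ITT.** SE = 3 × √(2/45) = 0.632. Let the true device difference (Dilapan-S minus Cook) be -2, exactly at the margin. Let cD and cC be the shares of the Dilapan-S and Cook arms that receive the other device. The ITT difference is then d = -2 × (1 - cD - cC), and

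P(declare non-inferiority) = 1 - Φ(1.96 - (2 + d)/0.632).

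| Assumed scenario, failures kept in ITT | d | Formula | Rank-sum simulation |
|---|---|---|---|
| No crossover | -2.0 | 2.5% | not run |
| 5% of Cook arm receives Dilapan-S | -1.9 | 3.6% | 3.5% |
| 10% of Cook arm receives Dilapan-S | -1.8 | 5.0% | 4.7% |
| 10% fail in each arm; half cross over, half get a third agent of midway effect | -1.7 | 6.9% | 6.5% |
| 10% of each arm crosses over (ceiling) | -1.6 | 9.2% | 8.4% |
| 10% of Dilapan-S arm fails and stays unripened | -2.2 | 1.1% | 1.2% |

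The last row assumes mean changes of 4 with Cook, 2 with Dilapan-S and 0 if unripened: 0.9 × 2 - 4 = -2.2. It shows that the result can also move against the claim.

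**3. A per-protocol set when failure is unrelated to prognosis.** In the crossover scenarios its simulated rate stays at 2.5%. With 10% excluded, 45 × 0.90 = 40.5 per arm remain; with 15%, 38.25. Power with equal devices is 85.1% and 83.0% by the normal formula, or about 83% and 81% after the 0.955 adjustment. If the devices are equal and 10% cross over each way, the two sets disagree in about 7% of trials by chance.

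**4. A per-protocol set when failure is related to prognosis.** Assume that 10% of women in each arm ripen 2 points less, and that those in the Dilapan-S arm fail placement and receive the Cook balloon. Per-protocol drops them from one arm only, so its difference is -2 + 0.10 × 2 = -1.8. Simulated rates are 4.8% for ITT and 4.7% for per-protocol. If these women ripen 4 points less, the rates are about 4% for ITT and 7% for per-protocol. If the 2-point group fails in the Cook arm instead, they are 4.3% and 1.3%. The per-protocol set can therefore err in either direction, and can err more than ITT.

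**The case against.** The strongest reply is that ITT is the right primary analysis and that the plan already has it. Section 3 builds the fallback into the study flow, which supports the policy reading, and on that reading none of the rates above is an error. This stands: the rates are errors only for the device-once-placed question.

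A reader might infer that the plan contradicts itself over whether failed placements stay in, because the 15% inflation seems to treat them as lost. The documents do not support that. ITT in its ordinary meaning keeps them in, and the inflation covers failed placement and loss to follow-up together, so it can be read as a cushion. The wording is loose, and that alone would not justify this point.

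A reader might also take 9.2% as the expected error. It is a ceiling that needs every failure in both arms to cross over. Appendix A names only balloon-to-Dilapan replacement; the reverse is possible only under section 3's general wording. Section 9 attributes failures partly to intolerance of the exam, and some of those women may not accept a second cervical device.

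Finally, it is tempting to say that a per-protocol analysis would reveal whether a small difference reflects similar devices or mixed arms. Step 4 shows that it cannot when placement failure is related to prognosis.

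**Conclusion.** The point holds in a limited form. The plan relies on ITT alone for a non-inferiority claim while permitting crossover to the test device. For the device-once-placed question, 5% to 10% balloon-to-Dilapan crossover raises the chance of a false claim from 2.5% to between 3.6% and 5.0%.

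These figures assume a true difference exactly at the margin, SD 3, 45 per arm, a one-sided 2.5% level and failures kept in their assigned arm. The actual crossover rate, the failure rate by arm and hence the direction of any shift cannot be known from the documents. The documents do not show that ITT is invalid or that the claim would be false. What is missing is a pre-specified supportive analysis that lets readers see how far the result depends on the women who did not receive their assigned device.

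**What to change.** In section 9:

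- Keep ITT as primary and define it: all randomised women in their assigned arm, including those with failed placement. Use the Bishop score at return to labor and delivery whether or not a device was placed, and report by arm any woman with no such exam. Restricting the set to women with an exam would make it a complete-case analysis.
- Pre-specify a supportive per-protocol analysis with the same method and the same margin of 2. It includes women whose assigned device was placed, who had no other ripening agent before the return exam, and whose return exam was done.
- Tabulate placement failure and device received by arm.
- State that a device-level non-inferiority conclusion will be worded with caution if the two sets disagree, and that disagreement will not be attributed to mixed arms.

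The cost is one paragraph, one table and one further run of the same analysis. Placement failure must already be recorded for the success composite. A supportive analysis takes no power from the primary claim and fits within the planned 90 participants.

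The downside is that per-protocol selects after randomisation and can be biased, so it must not decide the claim. Requiring both sets to succeed would be a different design: with equal devices and 10% crossing over each way, simulated joint power is about 81% against 86% for ITT alone, and about 78% against 84% with a further 5% loss to follow-up. Fallback clinical care is unchanged.

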study staff will then discuss the study in more detail, answer any questions, then will step away while NST is being performed (20-30 minutes) to allow for contemplation then will re-approach the subject to confirm if they are or are not interested in the study after NST is complete. After it is confirmed that the patient is still candidate for outpatient cervical ripening per standard practice at Brigham and Women's, which requires the non-stress test fetal heart tracing to be reactive, an exam to confirm the cervix needs ripening (Bishop score < 6 and cervix < 2cm dilated) and an ultrasound to confirm cephalic presentation, they will be randomized to either Dilapan-S or Cook balloon in a 1:1 ratio.

At the time of enrollment, patients will be assured that they will receive standard of care treatments whether or not they are in the study and enrollment will not affect their care.

Only adults will be included in the study. Study will be limited to English speaking patients as enrollment may happen day or night and on weekends (given outpatient cervical ripening schedule on labor and delivery) when interpreters may not be available. No surrogate decision makers will be allowed to consent for patients.

A random number generator will be used to randomize women in blocks of 6 with stratification based on parity (patients who have had a vaginal delivery before or not).

As randomization will occur after sterile vaginal exam, the examiner obtaining the initial exam will be blinded to which arm of the study the patient will be in as the exam will be recorded prior to randomization. The patient will not be blinded as the devices are different in placement and post-placement.

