6. STUDY PROCEDURES

Upon presentation for cervical ripening, a non-stress test will be performed per BWH outpatient ripening protocol. Then a sterile vaginal exam will be completed to assign Bishop score, as per standard routine. A bedside ultrasound will be completed to confirm fetus is still in the vertex presentation. The patient will then be consented if they have a reactive non-stress test, a Bishop score <6 and cervical exam <3cm dilated with confirmed vertex fetus. Once the patient has been consented and randomized, the participant will have a Cook catheter or Dilapan-S by direct visualization with a speculum, For the Cook catheter, the uterine component of the balloon will be inflated to maximum 60mL, the vaginal balloon will not be inflated per standard practice at BWH and per the literature that shows slightly increased pain and negligible improvement in cervical ripening. The catheter will be taped to the inner thigh with gentle traction. For Dilapan-S, 3-5 dilators will be placed per BWH protocol.

After placement, the patient will be discharged home with strict return precautions per the BWH outpatient cervical ripening protocol. With written instructions of who to call/page, with phone number listed, list of concerns that should prompt calling / return to hospital: Fever > 100.4 Fahrenheit, labor, rupture of membranes, reduced fetal movement vaginal bleeding, what to do if the balloon/rods fall out, exact time and place to return. Patients must return to labor and delivery within 24 hours of cervical ripening agent placement at their scheduled inpatient induction time.

Upon return to labor and delivery, if not already expelled, the mechanical ripening device will be removed, and an examiner **blinded to the cervical ripening method** will complete a sterile vaginal exam to assign a Bishop score.

The patient satisfaction survey will be completed by the patient at this time in paper form and collected by study staff.

At that point health care providers will manage active labor per usual practice. Labor interventions are at the discretion of the healthcare provider. The need for operative delivery or cesarean section will be at the discretion of the healthcare provider.

Secondary outcome information will be obtained from the Epic record including delivery, maternal and neonatal outcomes as defined in the statistical analysis below.

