If the patient satisfaction survey is not completed during the delivery admission, it may be collected anytime the patient returns to the hospital for routine prenatal care until the 6 week postpartum visit.

7. Risks and Discomforts

Women may experience discomfort with either Cook catheter or Dilapan-S insertion, though there is no increased risk from the standard BWH outpatient cervical ripening protocol.

Because both the Cook catheter and Dilapan-S are both routinely used for outpatient cervical ripening, we think that there is minimal increased risk from the study versus routine standard of care for outpatient cervical ripening.

8. Benefits

There is no direct benefit to individuals. There are however many benefits for the healthcare system in the future. By determining that Dilapan-S is noninferior to Cook catheter for outpatient cervical ripening we will be increasing provider awareness of an effective method of cervical ripening. Healthcare cost would benefit from the information gained in this study by potentially increasing outpatient cervical ripening which could decrease hospital stays. Currently, the most effective method of inducing labor remains unknown.

9. Statistical Analysis

The main outcome will be change in Bishop score. We will collect any information about outcomes regarding maternal or neonatal morbidity until four weeks from delivery. The patient satisfaction survey may be administered until the 6-week postpartum visit. Once these items are collected, patient participation will end.

Bishop score is defined by 5 components (Figure 3) all assessed during a sterile vaginal exam. These individual scores are then combined into a single score (0-13) to determine the Bishop score. Our

outcome of interest is change in Bishop score to be calculated as Bishop score after cervical ripening minus Bishop score prior to cervical ripening.

Figure 3. Bishop score. Final score is a sum of the 5 individual scores.

Score	Dilation (cm)	Position of Cervix	Effacement (%)	Station (-3 to +3)	Cervical Consistency
0	Closed	Posterior	0-30	-3	Firm
1	1-2	Mid-position	40-50	-2	Medium
2	3-4	Anterior	60-70	-1,0	Soft
3	5-6	--	80-100	+1 to +3	--

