The principal investigator will review the entries for each participant to ensure they are complete. We will not perform any interim analysis, as we feel there is minimal risk from the study protocol and would not stop the study early. When adverse events occur, they will be reported to the Partners' IRB within 5 days with a detailed description of the event as described in the guidelines for

adverse events reporting. Serious adverse events (severe hemorrhage, maternal death, neonatal death, neonatal hypoxemic encephalopathy) will be reviewed by the head of labor and delivery and the study staff to ensure the outcome is not related to the study protocol.

11. Privacy and Confidentiality

- Study procedures will be conducted in a private setting
- Only data and/or specimens necessary for the conduct of the study will be collected
- Data collected (paper and/or electronic) will be maintained in a secure location with appropriate protections such as password protection, encryption, physical security measures (locked files/areas)
- Specimens collected will be maintained in a secure location with appropriate protections (e.g. locked storage spaces, laboratory areas)- **No specimens collected**
- Data and specimens will only be shared with individuals who are members of the IRB-approved research team or approved for sharing as described in this IRB protocol
- Data and/or specimens requiring transportation from one location or electronic space to another will be transported only in a secure manner (e.g. encrypted files, password protection, using chain-of-custody procedures, etc.)
- All electronic communication with participants will comply with Mass General Brigham secure communication policies- **No electronic communication will occur**
- Identifiers will be coded or removed as soon as feasible and access to files linking identifiers with coded data or specimens will be limited to the minimal necessary members of the research team required to conduct the research
- All staff are trained on and will follow the Mass General Brigham policies and procedures for maintaining appropriate confidentiality of research data and specimens
- The PI will ensure that all staff implement and follow any Research Information Service Office (RISO) requirements for this research
- Additional privacy and/or confidentiality protections

12. References

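### The primary comparison is adjusted for parity only; adding the Bishop score recorded before randomisation is a cheap precision step with a probably small gain, not the repair of an error

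*Combined protocol and SAP*

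**What the plan says.** Section 9 defines the primary outcome as "change in Bishop score to be calculated as Bishop score after cervical ripening minus Bishop score prior to cervical ripening". On the analysis it says "Non-parametric measures will be used for statistical analysis", followed by "These models will also be adjusted for parity". No test or model is named, and parity is the only covariate. The design figures are given as "We have defined a non-inferiority margin of 2 with a standard deviation of 3 consistent with prior literature", leading to 39 per arm and, after a 15% increase, 45 per arm.

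The baseline score exists for everyone before allocation. Section 6 (Study Procedures) says of the visit: "Then a sterile vaginal exam will be completed to assign Bishop score, as per standard routine". Section 5 (Subject Enrollment) adds that "the exam will be recorded prior to randomization". Section 5 also makes parity the only stratification factor.

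**The concern.** Non-inferiority is decided by where one confidence limit falls against 2 points, in a trial of 78 evaluable women. The most obvious prognostic variable for the post-ripening score is the pre-ripening score. It enters the analysis only through subtraction, which sets its coefficient to 1 rather than estimating it. If the post score rises less than one-for-one with baseline (examination error in a score built from five judged components could do this), or more than one-for-one, some variance in the comparison could be removed with data already collected. What is at stake is precision. Chance imbalance in baseline is already reflected in the width of the interval, so there is no bias to correct.

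**Working it through.** **Inputs.** From section 9: margin 2, SD 3, two-sided 0.05, 80% power, 39 per arm. Assumed, because the documents do not give them: the SD of 3 refers to the change; the true difference is 0; the baseline SD *s* is 1.0 to 1.71 (1.71 is an even spread over scores 0 to 5); the slope *b* of post score on baseline is varied.

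**The plan's own figure.** A noncentral-*t* calculation needs 37 per arm. Dividing by the Wilcoxon efficiency 3/π gives 37 × π/3 = 38.7, so 39, which fits the planned non-parametric analysis. Then 39 × 1.15 = 44.85, so 45. The stated size is reproduced without any baseline adjustment.

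**Removable variance.** Write post = a + *b*·pre + error. The change is then a + (*b* − 1)·pre + error, and the part of its variance due to baseline is k = (1 − *b*)²*s*². For parity uncorrelated with baseline:

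- Parity only: variance 9, 75 df. Half-width = 1.992 × √(9 × 2/39) = 1.35. Power 82.8%.
- Parity and baseline: variance (9 − k) × 75/74, 74 df. The factor 75/74 pays for the extra coefficient.

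Example, *b* = 0.5 and *s* = 1.71: k = 0.25 × 2.924 = 0.731; (9 − 0.731) × 75/74 = 8.381; saving 1 − 8.381/9 = 6.9%; half-width 1.993 × √(8.381 × 2/39) = 1.31.

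| Slope | Net variance saved (*s* = 1.0; 1.71) | Power | 95% half-width |
|---|---|---|---|
| 0.5 or 1.5 | 1.5%; 6.9% | 83.3%; 85.3% | 1.34; 1.31 |
| 0.7 or 1.3 | −0.3%; 1.6% | 82.7%; 83.4% | 1.36; 1.34 |
| 1 | −1.4% | 82.3% | 1.36 |
| 0 (post unrelated to baseline) | 9.9%; 32% | 86.5%; 94.0% | 1.28; 1.12 |

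**Break-even.** (9 − k) × 75/74 = 9 gives k = 0.12, so |1 − *b*| = 0.346/*s*. The two break-even slopes are 0.65 and 1.35 for *s* = 1.0, and 0.80 and 1.20 for *s* = 1.71. Between them adjustment does not help.

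**Sensitivity, at slope 0.5.**

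- With all 45 per arm evaluable, power goes from 87.8% to 88.4–90.0%.
- If baseline correlates 0.5 with parity, the saving is 0.8–4.9%, because parity already carries part of it.
- If 3 is the SD of the post score rather than of the change, the figures are the same.
- If a score of 6 can enter, an even spread over 0 to 6 has SD 2.0 and the saving is 9.9%. Section 3 excludes only "No need for cervical ripening (Bishop score >6, >2cm dilated"), whereas sections 5 and 6 require a score below 6; these passages need reconciling.

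**Rank model.** This was simulated with 39 per arm, integer scores and 20,000 runs per setting. Two points were added to each Dilapan-S change, and the ranks were modelled on arm and parity, then with baseline added. Power for *s* = 1.0 and *s* = 1.71 in turn:

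- Slope 0.5: 81.0% to 81.5%, and 80.6% to 83.2%.
- Slope 0.7: 80.3% to 79.9%, and 80.6% to 81.1%.
- Slope 1: 81.0% to 80.5%, and 81.6% to 81.0%.

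**Validity.** In a separate linear-model simulation (6,000 runs per setting), the parity-only analysis had a mean error of at most 0.02 points and one-sided type I error of 2.2–2.6%. With baseline added, type I error was 2.4–2.7%.

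**The case against.** The strongest reply is that nothing is broken. Baseline is already used through subtraction, parity adjustment matches the stratification, and the stated sample size does not depend on this covariate. All of that stands. It is also true that the size, and even the sign, of the effect rests on a slope and a baseline SD that the documents do not give. At slope 0.5 the half-width shrinks by only 0.01 to 0.04 points against a margin of 2. What remains is an asymmetry: the worst case is tiny and the possible gain is larger, for one added sentence and no new data.

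A second objection concerns the analysis family. The plan names no model, and its non-parametric intention does not by itself yield an interval in points. This also stands. A rank analysis of covariance after the 2-point shift can take baseline as a covariate but gives only a test.

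A reader might infer that the entry limit on the Bishop score shows a slope below 1. It does not. The limit narrows the baseline spread and so caps the gain; it says nothing about the slope. A reader might also take the 10–32% savings as the expected benefit. They require a post score unrelated to baseline, or a slope far above 1 (at a pre/post correlation of 0.7, which implies slopes of about 1.6 to 2.5 here, 12–26% before the cost of the extra coefficient). The documents support neither.

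**Conclusion.** This is an optional improvement. The parity-adjusted comparison is unbiased and holds its error rate, and it would be wrong to read the omission as bias, as an invalid analysis or as an underpowered design.

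Under the stated assumptions, a slope of 0.5 or 1.5 gains about 0.5 to 2.5 percentage points of power in a linear model. In the rank model, simulated at slope 0.5, the gain is about 0.5 to 2.6 points. Between break-even slopes of about 0.65–0.80 and 1.20–1.35 there is no gain, or a loss of at most 1.4% of variance. "Probably small" is a judgement about plausible slopes, not something the documents establish, so confidence in the size is moderate.

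**What to change.** In section 9, keep "These models will also be adjusted for parity" as it stands, since it speaks of models in the plural and replacing it could remove parity adjustment from the secondary analyses. Add after it:

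> The primary non-inferiority model will additionally be adjusted for the Bishop score recorded before randomisation.

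If a narrower interval is the aim, the primary model must estimate the adjusted difference in points (Dilapan-S minus Cook) with a 95% confidence interval set against −2. A linear model does this but departs from the stated non-parametric approach. A rank analysis of covariance stays within that approach and gives a test only. Choosing and naming the model is a separate decision, and the covariate can be added under either.

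The sentence must be fixed before outcomes are compared by arm. Section 10 states "We will not perform any interim analysis", so no such comparison is planned before the end, but the documents do not show whether one has already been made. If it has, the adjusted analysis should be labelled post hoc.

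The cost is one degree of freedom: at worst about 1.4% of variance, or half a percentage point of power, if the true slope is 1. No new data are needed and the sample size does not change.
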